6.2.3. Laboratory Safety Tests

Safety laboratory tests will be performed as described in the protocol.

To determine if there are any clinically significant laboratory abnormalities, the haematological, clinical chemistry (serum) and urinalysis safety tests will be assessed against the criteria specified in the sponsor reporting standards. The assessment will take into account whether each subject’s baseline test result is within or outside the laboratory reference range for the particular laboratory parameter.

Baseline will be the last predose measurement of before the first dose of any component of the study treatment.

6.2.4. Vital Signs

Vital signs will include measurements of blood pressure, pulse, and temperature (oral, temporal, ear). On dosing days, vital signs should be measured prior to administration of any of the study treatments. Sitting blood pressure (BP) and pulse after approximately 5 minutes rest, will be measured with the patient’s arm supported at the level of the heart and recorded to the nearest mmHg sufficient. The same arm (preferably the dominant arm) should

preferably be used throughout the trial. A blood pressure cuff, which has been properly sized and calibrated, should be used to measure blood pressure. The use of automated devices for measuring BP is acceptable. Vitals signs, including temperature, pulse, and BP to be recorded 1-hour post-study drug administration during each Cycle on Days 1, 29, 57, and 85. Baseline vital sign will be the last predose measurement of before the first dose of any component of the study treatment.

6.2.5. ECG

Electrocardiogram machines to be utilized in this study will be supplied by a third party vendor.

At screening, a single 12-lead ECG tracing (with a 10-second rhythm strip) will be obtained. For Cycle 1 Day 1 and all subsequent specified time points (see Schedule of Activities in the protocol), triplicate 12-lead ECG tracings (with a 10-second rhythm strip) will be obtained.

Generally, baseline and all corresponding time point ECGs should not be collected within 3 hours after food or beverage consumption and should be performed after the patient has rested quietly for at least 10 minutes in a supine position. All 12 lead ECGs should be confirmed by a qualified person at the institution and will be reviewed by a central laboratory.

At each time point, (see the Schedule of Activities), three consecutive ECGs will be performed at approximately 2 minutes apart to determine the mean QTcF interval. If the mean QTcF is prolonged (value of >500 msec), the ECGs should be re-evaluated by a qualified person at the institution for confirmation. If manual reading verifies a QTcF of >500 msec, immediate correction for reversible causes (including electrolyte abnormalities, hypoxia and concomitant medications for drugs with the potential to prolong the QTcF interval) should be performed. In addition, repeat ECGs should be immediately performed hourly for at least 3 hours until the QTcF interval falls below 500 msec. If QTcF interval reverts to less than 500 msec, and in the judgment of the investigator(s) and sponsor it is determined to be due to cause(s) other than investigational product, treatment may be continued with regular ECG monitoring. If in that timeframe the QTcF intervals rise above 500 msec the investigational product will be held until the QTcF interval decreases to 500 msec. Patients will then re-start the investigational product at the next lowest dose level.

If the QTcF interval has still not decreased to 500 msec after 2-weeks, or if at any time a patient has a QTcF interval >515 msec or becomes symptomatic, the patient will be removed from the study. Additional triplicate ECGs may be performed as clinically indicated.

Prior to concluding that an episode of prolongation of the QTcF interval is due to investigational product, thorough consideration should be given to potential precipitating factors (eg, change in patient clinical condition, effect of concurrent medication, electrolyte disturbance) and possible evaluation by specialist.

If the patient experiences a cardiac or neurologic AE (specifically syncope, dizziness, seizures, or stroke), an ECG (triplicate) should be obtained at the time of the event.

Prior to concluding that an episode of prolongation of the QTcF interval is due to investigational product, thorough consideration should be given to potential precipitating factors (eg, change in patient clinical condition, effect of concurrent medication, electrolyte disturbance) and possible evaluation by specialist.

When matched with PK sampling, the ECG must be carried out before each PK sample drawing such that the PK sample is collected at the nominal time (ie, the timing of the PK collections over rides the timing of the ECG collections).

Baseline is defined as the pre-dose ECG collected before the first dose of any component of the study treatment.

6.2.6. Other Safety Data

Additional safety data will be collected as described in the protocol and will be listed if collected in the sponsor's database.

6.3. Pharmacokinetic Parameters

Tremelimumab single-dose PK parameters, including the maximum concentration (C_{max}), time to maximum concentration (T_{max}), and area under the concentration versus time curve (AUC) from time zero to the last quantifiable time point prior to the second tremelimumab dose (AUC_{last}) and if data permit, AUC from time zero extrapolated to infinity (AUC_{inf}); and trough concentrations after multiple dosing (C_{trough}).

PF-06801591 single-dose PK parameters, including C_{max} , T_{max} , AUC_{last} , and if data permit, AUC_{inf} ; and C_{trough} after multiple dosing.

6.4. PD Endpoints

None.

6.5. Other Endpoints

None.

6.6. Covariates

None.

7. HANDLING OF MISSING VALUES

For the analysis of safety endpoints, the sponsor data standard rules for imputation will be applied.

7.1. Concentrations Below the Limit of Quantification

In all data presentations (except listings), concentrations below the limit of quantification (BLQ) will be set to zero. (In listings BLQ values will be reported as “<LLQ”, where LLQ will be replaced with the value for the lower limit of quantification).

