9.6. Analysis of Pharmacokinetics CCI

9.6.1. Analysis of Pharmacokinetics

9.6.1.1. Tremelimumab Pharmacokinetic Analysis

The concentration -time data for tremelimumab will be summarized descriptively (n, mean, standard deviation, coefficient of variation (CV), median, minimum, maximum, geometric mean and its associated CV) by dose, and nominal time for both Part 1 and Part 2.

For participants assigned to Cohorts 3A and 6A , the concentration -time data of tremelimumab after the first dose will be analyzed individually by noncompartmental methods to determine PK parameters. The PK parameters to be estimated will include the maximum plasma concentration (C_{max}), time to maximum plasma concentration (T_{max}), and area under the plasma concentration versus time curve following the first dose from time 0 to the last time point prior to the second tremelimumab dose (AUC_{last}) and if data permit or if considered appropriate, area under the plasma concentration versus time curve from time 0 extrapolated to infinity (AUC_{inf}), terminal elimination half-life- ($t_{1/2}$), apparent serum clearance (CL/F), apparent volume of distribution (V_z/F). The PK parameters will be summarized descriptively (n, mean, standard deviation, coefficient of variation (CV), median, minimum, maximum, geometric mean and its associated CV) by dose.

Individual participant and median profiles of the concentration time data, after the first tremelimumab dose, will be plotted by dose, using nominal times. Individual and median profiles will be presented on both linear-linear and log-linear scales.

[figure not shown]

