8.2.1.1. Tremelimumab and PF-06801591 Pharmacokinetics

Presentation of Tremelimumab and PF-06801591 concentration-time data:

The concentration-time data of tremelimumab and PF-06801591 will be presented as below:

- A listing of all concentrations by cohort, subject ID and nominal time for each compound. The concentration listings will also include the actual times. Deviations from the nominal time will be given in a separate listing for each compound;
- A summary of concentrations for each compound by cohort and nominal time, where the set of statistics will include n, mean, standard deviation, median, coefficient of variation (cv), percentage cv, minimum, maximum, geometric mean, and the number of concentrations above the lower limit of quantification;
- For the concentration-time data after the first dose, median concentrations time plots (on both linear and semi-log scales) against nominal time postdose by cohort (all cohorts on the same plot per scale, based on the summary of concentrations by cohort and time postdose) for tremelimumab (for Cohorts 3A through 7A) and PF-06801591 (for Cohorts 4A through 7A);
- For the concentration-time data after the first dose mean concentrations time plots (on both linear and semi-log scales) against nominal time postdose by cohort (all cohorts on the same plot per scale, based on the summary of concentrations by cohort and time postdose) for tremelimumab (for Cohorts 3A through 7A) and PF-06801591 (for Cohorts 4A through 7A).

For drug concentration summary statistics, median and mean plots by sampling time, the nominal PK sampling time will be used.

Calculation of PK parameters:

For patients of Cohorts 3A through 7A, the concentration-time data of tremelimumab after the first dose will be analyzed individually by non-compartmental methods to determine the PK parameters. For patients of Cohorts 4A through 7A, the concentration time data of PF-06801591 after the first dose will be analyzed individually by non compartmental methods to determine the PK parameters.

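### Setting BLQ concentrations to zero conflicts with the required geometric mean of concentrations (and, in the protocol, its CV): one BLQ value makes the mean zero or undefined

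*SAP*

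**What the plan says.** SAP 7.1 states that, in every data presentation other than listings, "concentrations below the limit of quantification (BLQ) will be set to zero". Listings show such values as below the LLQ instead. No other exception is made.

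SAP 8.2.1.1 lists the statistics for concentrations by cohort and nominal time. The list ends with "geometric mean, and the number of concentrations above the lower limit of quantification", and its measures of spread are the standard deviation and the ordinary CV. The same section requires "median concentrations time plots (on both linear and semi-log scales) against nominal time postdose by cohort", and the same for means, both for data after the first dose.

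Protocol 9.6.1.1 asks for tremelimumab concentrations to be summarised with "geometric mean and its associated CV) by dose, and nominal time for both Part 1 and Part 2", and 9.6.1.2 asks the same for sasanlimab. On plots after the first dose, protocol 9.6.1.1 says: "Individual and median profiles will be presented on both linear-linear and log-linear scales". The protocol has no BLQ rule of its own.

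SAP 7.2 suppresses summary statistics at a time point when more than half the data are missing. Missing there means not done, no sample, a sampling-time deviation of concern, or a value flagged as anomalous.

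**The concern.** A geometric mean is computed from logarithms, and zero has no logarithm. Once a BLQ value has been replaced by zero, the geometric mean at that time point cannot be computed from logs and equals zero in product form, whatever the other participants' values are. The instruction to use zero and the instruction to report a geometric mean cannot both give a meaningful number.

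The SAP 7.2 suppression rule does not help, because a BLQ value set to zero is a recorded value and not a missing one.

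What is at stake is a descriptive statistic for drug exposure. Trough concentration is a secondary endpoint in both parts (protocol 2.1 and 2.2). SAP Table 2 does not include Ctrough, so the concentration summary appears to be where troughs are reported. Part 1 cohorts are small (2 to 4 evaluable participants, up to 12 at the predicted MTD, SAP 2.1.2), so one value can decide the reported figure. If the SAP does not choose a rule, the choice is left to programming defaults or is made after the data are seen.

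**Working it through.** **Inputs.** The BLQ rule is from SAP 7.1, the required statistics from SAP 8.2.1.1 and protocol 9.6.1.1 and 9.6.1.2, and the cohort sizes from SAP 2.1.2. The documents state no LLQ, so 0.01, 0.1 and 1.0 (arbitrary units) are assumed to show a range. The plan gives no figure of its own to reproduce.

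**Formulas.** Geometric mean GM = exp[(1/n) Σ ln x], equivalently (Π x)^(1/n). Geometric CV = 100 × √(exp(s²) − 1), where s is the SD of ln x.

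**Example: eleven values of 5 and one BLQ, n = 12.**
- BLQ set to 0: the product is 0, so GM = 0; in log form ln 0 is undefined. s and the geometric CV are undefined.
- Arithmetic mean = 55/12 = 4.58 and median = 5. Both remain available.
- Zero dropped: GM = 5.0.
- LLQ/2, LLQ 0.01: exp[(11 ln 5 + ln 0.005)/12] = 2.8.
- LLQ/2, LLQ 0.1: exp[(11 ln 5 + ln 0.05)/12] = 3.4.
- LLQ/2, LLQ 1.0: exp[(11 ln 5 + ln 0.5)/12] = 4.1.

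**Second example: 8, 10, 12, 9, 11 and one BLQ, n = 6.** Under the zero rule the arithmetic mean is 8.33 and the median 9.5, but GM is 0 and the geometric CV is undefined. The alternatives are:

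| Rule | GM | Geometric CV |
|---|---|---|
| BLQ excluded | 9.90 | 16% |
| LLQ/2, LLQ 0.01 | 2.79 | 12,296% |
| LLQ/2, LLQ 0.1 | 4.10 | 1,034% |
| LLQ/2, LLQ 1.0 | 6.02 | 187% |

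The same failure was confirmed at n = 3, 4 and 12.

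**Plots.** With zeros substituted, a median is zero only when more than half the values are BLQ, and an arithmetic mean only when all are. One BLQ value therefore does not remove a point from the SAP's semi-log mean or median plots. Individual log-linear profiles, which the protocol requires, lose each zero point.

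**When it arises.** Dosing-day samples are drawn within 6 hours before dosing (footnotes to both PK schedules in the protocol). The Cycle 1 Day 1 sample therefore precedes any study drug, and BLQ is expected in nearly everyone. After dosing, the rate is unknown. The chance of at least one BLQ value at a time point is 1 − (1 − p)^n, assuming independence:

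| Assumed BLQ rate p | n = 3 | n = 6 | n = 12 |
|---|---|---|---|
| 5% | 14% | 26% | 46% |
| 10% | 27% | 47% | 72% |
| 20% | 49% | 74% | 93% |

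These rates are assumptions, not estimates from the trial.

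**The case against.** The strongest reply is that this touches one descriptive statistic. The table also carries n, arithmetic mean, SD, median, minimum, maximum and the number above the LLQ, so a reader can see that BLQ values exist and still has usable summaries. No hypothesis test, dose decision or primary endpoint uses the geometric mean. All of that stands, and it limits the importance of the point.

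Other limits also stand:
- The SAP asks for a geometric CV only for PK parameters (Table 2). For concentrations that requirement comes from the protocol, and SAP section 2 says that the SAP supersedes the protocol's statistical considerations.
- The SAP was written for Part 1 under the protocol of 16 March 2018. Carrying its zero rule into Part 2 is an extrapolation, though the protocol asks for the same statistic there.
- The one nearly certain case, pre-dose Cycle 1 Day 1, is trivial, because no exposure conclusion rests on it.
- Exposure lowered by anti-drug antibodies is documented only in the monkey study (protocol 1.4.1). Human BLQ rates are not given.
- LLQ/2 is not obviously right, since the tables above show how strongly it depends on the assay limit.

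None of this removes the conflict. The count above the LLQ shows that BLQ values are present, but it does not say how the geometric mean is to be computed.

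**Conclusion.** The conflict is real and narrow. As written, the zero rule gives a geometric mean of 0 or undefined, and an undefined geometric CV, at every time point with at least one BLQ value. This is a stated rule giving a wrong result, not merely missing detail. It follows from the text and the formula without any assumption. How often it would happen after dosing, and the numerical effect of each alternative, do rest on assumed BLQ rates and LLQs.

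A reader might infer that the trough summary as a whole is invalid, or that the semi-log plots fail with one BLQ value. The documents do not support either reading: the other summaries remain computable, and the mean and median plots fail only where the plotted value is zero. A reader might also infer that the reported geometric means will be biased upward. That would happen if software silently dropped the zeros, but the documents do not describe the programming. The supportable conclusion is that one secondary descriptive statistic needs a workable rule, set in advance.

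**What to change.** Amend SAP 7.1 as follows.

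1. Keep zero for arithmetic means, medians and linear-scale plots.
2. Exempt geometric mean, geometric CV and log-scale plots from the zero rule, and prespecify one rule for them. As the default, do not calculate the geometric statistics at a time point with any BLQ value, and show the BLQ count. Alternatives are a stated substitution such as LLQ/2 or a censored-data method. With either, show the BLQ count and suppress the statistic where more than half the values are BLQ.
3. Omit the pre-dose Cycle 1 Day 1 time point from geometric statistics and log-scale plots.
4. Carry the same rule into the Part 2 SAP, where Ctrough is a secondary endpoint.

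The cost is a few sentences and a minor programming change. The downside is that the geometric mean is not shown at some time points under the default, or depends on the chosen substitution under that alternative.

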7.2. Deviations, Missing Concentrations and Anomalous Values

In summary tables and plots of median profiles, statistics will be calculated having set concentrations to missing if 1 of the following cases is true:

1. A concentration has been collected as ND (ie, not done) or NS (ie, no sample):
2. A deviation in sampling time is of sufficient concern or a concentration has been flagged anomalous by the pharmacokineticist.

Note that summary statistics will not be presented at a particular time point if more than 50% of the data are missing.

7.3. Pharmacokinetic Parameters

For both tremelimumab and PF-06801591, actual PK sampling times will be used in the derivation of PK parameters.

If a PK parameter cannot be derived from a subject's concentration data, the parameter will be coded as NC (ie not calculated). (Note that NC values will not be generated beyond the day that a subject discontinues).

In summary tables, statistics will be calculated by setting NC values to missing; and statistics will be presented for a particular dose with ≥ 3 evaluable measurements. In summary tables, statistics will be calculated by setting NC values to missing; and statistics will not be presented for a particular treatment if more than 50% of the data are NC. For statistical analyses (ie analysis of variance), PK parameters coded as NC will also be set to missing.

8. STATISTICAL METHODOLOGY AND STATISTICAL ANALYSES

8.1. Statistical Methods

CCI

Part

2 (dose expansion) will require a protocol amendment; only a high level study design is described in the protocol. For the mTNBC cohort, the study will enroll n=26 patients and have approximately 80% power with 1-sided alpha=0.1 to detect an ORR of 50% with a null hypothesis of 30% ORR.

8.2. Statistical Analyses

8.2.1. Pharmacokinetic Analysis

Patients who receive the designated investigational product of interest and have at least one post-dose drug concentration measurement will be included in the PK data analysis. The actual time of sample collection will be used in PK parameter calculation. In the event that the actual sampling time is not available, the nominal time may be used if there is no evidence that the actual sampling time deviates substantially from the nominal time.

8.2.1.1. Tremelimumab and PF-06801591 Pharmacokinetics

Presentation of Tremelimumab and PF-06801591 concentration-time data:

The concentration-time data of tremelimumab and PF-06801591 will be presented as below:

- A listing of all concentrations by cohort, subject ID and nominal time for each compound. The concentration listings will also include the actual times. Deviations from the nominal time will be given in a separate listing for each compound;
- A summary of concentrations for each compound by cohort and nominal time, where the set of statistics will include n, mean, standard deviation, median, coefficient of variation (cv), percentage cv, minimum, maximum, geometric mean, and the number of concentrations above the lower limit of quantification;
- For the concentration-time data after the first dose, median concentrations time plots (on both linear and semi-log scales) against nominal time postdose by cohort (all cohorts on the same plot per scale, based on the summary of concentrations by cohort and time postdose) for tremelimumab (for Cohorts 3A through 7A) and PF-06801591 (for Cohorts 4A through 7A);
- For the concentration-time data after the first dose mean concentrations time plots (on both linear and semi-log scales) against nominal time postdose by cohort (all cohorts on the same plot per scale, based on the summary of concentrations by cohort and time postdose) for tremelimumab (for Cohorts 3A through 7A) and PF-06801591 (for Cohorts 4A through 7A).

For drug concentration summary statistics, median and mean plots by sampling time, the nominal PK sampling time will be used.

Calculation of PK parameters:

For patients of Cohorts 3A through 7A, the concentration-time data of tremelimumab after the first dose will be analyzed individually by non-compartmental methods to determine the PK parameters. For patients of Cohorts 4A through 7A, the concentration time data of PF-06801591 after the first dose will be analyzed individually by non compartmental methods to determine the PK parameters.

For each compound, the PK parameters to be estimated will include the maximum drug concentration (C_{max}), time to maximum drug concentration (T_{max}), and area under the concentration versus time curve (AUC) from time zero to the last quantifiable time point prior to the second tremelimumab or PF-06801591 dose (AUC_{last}), and if data permit, AUC from time zero extrapolated to infinity (AUC_{inf}), terminal elimination half-life ($t_{1/2}$), and apparent clearance (CL/F).

In addition, the accumulation ratio (R_{ac}) as calculated by the ratio of the trough concentration prior to the fifth tremelimumab or PF-06801591 dose (on Cycle 2 Day 1) to the concentration prior to the second tremelimumab or PF-06801591 dose (on Cycle 1, Day 29) will be determined individually if data permit.

PK parameters will be calculated using standard non-compartmental methods:

Parameter	Method of Determination
AUC_{last}	Linear/log trapezoidal method
AUC_{inf}^a	$AUC_{last} + C_{last}/k_{el}$, where C_{last} is the predicted concentration at the last quantifiable timepoint (T) estimated from the log-linear regression analysis, and k_{el} is the terminal phaser rate constant by a linear regression of the log-linear concentration time curve. The terminal log-linear phase will be determined from a minimum of 3 concentration time data points and will be verified with r^2 value.
C_{max} , T_{max}	Observed directly from data
CL/F	Dose/ AUC_{inf}
$t_{1/2}$	$\ln 2/k_{el}$

^aif data permit.

Each PK parameter will be summarized by dose and will include the set of summary statistics as specified in the table below:

Table 2. PK Parameters to be Summarized Descriptively

Parameter	Summary Statistics
AUC_{last} , AUC_{inf} , C_{max} , CL/F and V_Z/F	N, arithmetic mean, median, $cv\%$, standard deviation, minimum, maximum, geometric mean and geometric $cv\%$.
T_{max}	N, median, minimum, maximum.
$t_{1/2}$	N, arithmetic mean, median, $cv\%$, standard deviation, minimum, maximum.

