Protocol Activity	Screen (£28 days)	Treatment Period											Post Treatment			
		Cycle 1							Cycle 2				End of Treatment	Follow- Up (Months after EOT visit)		
Study Day		Day 1	Day 3 -6	Day 8	Day 15	Day 22	Day 29	Day 43	Day 57	Day 71	Day 85	Day 113				
Cycle Day												Day 1	Day 29	Day 57	Day 85	Day 99
Visit Window (hours)			±24 hr	±48 hr	±48 hr											
Visit Window (days)						±2	±4	±2	±4	±2	±2	±2	±2	±2	±4	±4
Study Treatment																

Abbreviations: ADA = Anti-drug antibody; Adenovirus (AdC68); EOT = End of Treatment; pDNA = Plasmid deoxyribonucleic acid, PK = Pharmacokinetics

1. Adenovirus (AdC68) will be administered intramuscularly on Cycle 1 Day 1 and Cycle 2 Day 1. Tremelimumab and sasanlimab will be administered after the adenovirus for participants assigned to receive these components.
2. Plasmid DNA (pDNA) vaccinations will be administered intramuscularly using an electroporation device on Day 29, Day 57 and Day 85 of each cycle. Tremelimumab and sasanlimab will be administered after the pDNA for participants assigned to receive these components. All pDNA vaccinations should be administered prior to administering the tremelimumab and sasanlimab.
3. Tremelimumab will be administered subcutaneously in close proximity to the vaccine injected muscle and vaccine draining lymph nodes on Day 1, Day 29, Day 57 and Day 85 of each cycle. Tremelimumab will be administered after the adenovirus or pDNA and, for participants assigned to receive sasanlimab, before the sasanlimab. Both tremelimumab injections should be administered prior to administering the sasanlimab.
4. Sasanlimab will be administered subcutaneously in close proximity to the vaccine injected muscle and vaccine draining lymph nodes on Day 1, Day 29, Day 57 and Day 85 of each cycle. Sasanlimab will be administered after the adenovirus or pDNA and after the tremelimumab.
5. Blood samples for determination of tremelimumab drug concentrations and for detection of ADA/NAb against tremelimumab will be collected as outlined in the [schedule of activities](#). Samples to be collected on dosing days are to be obtained within 6 hours prior to tremelimumab dosing.
6. For participants assigned to Cohorts 3A, 6A, and 7A only.

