7. Blood samples for determination of sasanlimab drug concentrations and for detection of ADA/NAb against sasanlimab will be collected as outlined in the [schedule of activities](#). Samples to be collected on dosing days are to be obtained within 6 hours prior to sasanlimab dosing.
8. For participants assigned to Cohorts 4A and 5A only.

SCHEDULE OF ACTIVITIES FOR DOSE EXPANSION (PART 2)

Protocol Activity	Screen ¹ (≤28 days)	Treatment Period												End of Treatment ³²	Post Treatment				Survival Follow-up ³⁴	
		Cycle 1						Cycle 2							Follow- Up (Months after EOT visit)					
Study Day		Day 1	Day 8	Day 15	Day 22	Day 29	Day 43	Day 57	Day 71	Day 85	Day 113				Month 1 ³³	Month 2	Month 4	Month 6	Post 6-Month Follow-up	
Cycle Day											Day 1	Day 29	Day 57	Day 85	Day 99		28 to 35 days			Every 3 Months
Visit Window (Days)*			±1	±2	±2	±2	±4	±2	±4	±2	±2	±2	±2	±2	±4		±4	±4	±4	±10
Informed consent ²	X																			
Tumor history ³	X																			
CCI																				
Medical history ⁷	X																			
Complete physical examination ⁸	X														X					
Abbreviated physical examination ⁸		X		X		X		X		X	X	X	X	X		X	X	X	X	
Assessment of skin thickness at administration sites ⁹	X																			
Height	X																			
Weight	X	X									X				X					
Vital signs ¹⁰	X	X	X	X	X	X		X		X	X	X	X	X	X	X	X	X	X	
Performance status ¹¹	X	X			X		X		X	X	X	X	X	X	X	X	X	X	X	
Laboratory																				
Unique Screening Labs ¹²	X																			
Hematology ¹³	X	X	X	X	X	X	X	X	X	X	X	X	X	X	X	X	X	X		
Blood Chemistry ¹⁴	X	X	X	X	X	X	X	X	X	X	X	X	X	X	X	X	X	X		
Coagulation ¹⁵	X			X		X		X		X					X	X				

PFIZER CONFIDENTIAL

Protocol Activity	Screen ¹ (≤28 days)	Treatment Period										End of Treatment ³²	Post Treatment				Survival Follow-up ³⁴			
		Cycle 1					Cycle 2						Follow- Up (Months after EOT visit)							
Study Day		Day 1	Day 8	Day 15	Day 22	Day 29	Day 43	Day 57	Day 71	Day 85	Day 113				Month 1 ³³	Month 2	Month 4	Month 6	Post 6-Month Follow-up	
Cycle Day											Day 1	Day 29	Day 57	Day 85	Day 99		28 to 35 days			Every 3 Months
Visit Window (Days)*		±1	±2	±2	±2	±4	±2	±4	±2	±2	±2	±2	±2	±2	±4	±4	±4	±10		
Cardiac Troponin-I (cTnI) ¹⁶	X				X		X		X		X									
Urinalysis ¹⁷	X			X		X		X		X	X	X	X	X	X	X				
Pregnancy Test or FSH Level (Serum) ¹⁸	X	X			X		X		X	X	X	X	X	X	X					
Contraception Check ¹⁹	X	X			X		X		X	X	X	X	X	X	X	X	X			
(12 lead) ECG ²⁰	X	X			X				X			X		X	X					
Registration																				
Registration ²¹		X																		

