9.6.1.2. Sasanlimab Pharmacokinetic Analysis

The concentration -time data for sasanlimab will be summarized descriptively (n, mean, standard deviation, CV, median, minimum, maximum, geometric mean and its associated CV) by dose, and nominal time for both Part 1 and Part 2.

For participants assigned to Cohorts 4A and 5A, the concentration -time data of sasanlimab after the first dose will be analyzed individually by noncompartmental methods to determine PK parameters. The PK parameters to be estimated will include the following: (a) the maximum plasma concentration (C_{max}), (b) time to maximum plasma concentration (T_{max}), and (c) area under the plasma concentration versus time curve following the first dose from time 0 to the last time point prior to the second sasanlimab dose (AUC_{last}). If data permit or if considered appropriate, other analyses may include: (a) area under the plasma concentration versus time curve from time 0 extrapolated to infinity (AUC_{inf}), (b) terminal elimination half-life ($t_{1/2}$), (c) apparent serum clearance (CL/F), and (d) apparent volume of distribution (V_z/F). The PK parameters will be summarized descriptively (n, mean, standard deviation, coefficient of variation (CV), median, minimum, maximum, geometric mean and its associated CV) by dose).

Individual participant and median profiles of the concentration-time data after the first sasanlimab dose will be plotted by dose using nominal times. Individual and median profiles will be presented on both linear-linear and log-linear scales.

CCI

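### SAP 8.2.1.1 runs first-dose NCA in cohorts that lack the Day 3-6 sample and pools them by dose with cohorts that have it

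*SAP*

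**What the plan says.** SAP 8.2.1.1 plans individual first-dose NCA for both antibodies. Tremelimumab: "For patients of Cohorts 3A through 7A, the concentration-time data of tremelimumab after the first dose will be analyzed individually". Sasanlimab: "For patients of Cohorts 4A through 7A, the concentration time data of PF-06801591 after the first dose will be analyzed individually". Cmax and Tmax are "Observed directly from data", and AUClast comes from a linear/log trapezoid. The data-permitting qualifier covers AUCinf, half-life and CL/F. It does not cover Cmax, Tmax or AUClast. Parameters are then summarised by dose.

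The current protocol is narrower. Section 9.6.1.1 introduces tremelimumab NCA with "For participants assigned to Cohorts 3A and 6A", and Section 9.6.1.2 introduces sasanlimab NCA with "For participants assigned to Cohorts 4A and 5A".

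The Part 1 schedule of study treatment and pharmacokinetics restricts the Day 3-6 sample by footnote. Footnote 6, on the tremelimumab sample, reads "For participants assigned to Cohorts 3A, 6A, and 7A only". Footnote 8, on the sasanlimab sample, reads "For participants assigned to Cohorts 4A and 5A only". Footnote 5 adds: "Samples to be collected on dosing days are to be obtained within 6 hours prior to tremelimumab dosing". Footnote 7 sets the same rule for sasanlimab.

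Protocol 3.1 records that Part 1 ended after six cohorts, so 7A was not run.

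**The concern.** The Day 1 sample is pre-dose. A cohort without the Day 3-6 sample therefore has its first post-dose concentration at the Day 8 visit, nominally 7 days after a subcutaneous dose. The trapezoid must then cover the whole rise with one straight line, and neither Cmax nor Tmax can register an earlier peak.

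The protocol's cohort lists avoid this. The SAP's lists do not, and its summary by dose then mixes two sampling schedules within one dose level. Cmax and Tmax are Part 1 secondary endpoints (protocol 2.1), and AUClast is a planned parameter (protocol 9.6.1, SAP 6.3). A difference between dose levels could partly reflect when blood was drawn.

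Other SAP rules do not catch it. The parameter set in SAP 5.2.2 admits anyone with at least one parameter. The not-calculated code in SAP 7.3 is not triggered, because a highest observed value and an area can always be derived from sparse data.

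**Working it through.** **1. Cohort lists.** Doses are taken from SAP 2.1.1 and protocol 3.1, with cohort numbers assigned in the order listed. This fits the SAP's starting cohorts of 3A for tremelimumab and 4A for sasanlimab.

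| Cohort | Tremelimumab | Day 3-6 sample | NCA: SAP / protocol | Sasanlimab | Day 3-6 sample | NCA: SAP / protocol |
|---|---|---|---|---|---|---|
| 3A | 40 mg | yes | yes / yes | none | n/a | n/a |
| 4A | 40 mg | no | yes / no | 130 mg | yes | yes / yes |
| 5A | 40 mg | no | yes / no | 300 mg | yes | yes / yes |
| 6A | 80 mg | yes | yes / yes | 300 mg | no | yes / no |
| 7A (not run) | 150 mg | yes | yes / no | 300 mg | no | yes / no |

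Among cohorts run, the SAP adds NCA for tremelimumab in 4A and 5A and for sasanlimab in 6A. None of these has the early sample. Summarised by dose, 40 mg tremelimumab mixes 3A (early sample) with 4A and 5A (none), and 300 mg sasanlimab mixes 5A (early sample) with 6A (none). The 80 mg tremelimumab and 130 mg sasanlimab summaries use early-sample cohorts only.

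**2. Direction, without a model.** Removing a sample can only lower the highest observed value or leave it unchanged. Tmax cannot fall before the Day 8 visit.

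**3. Size, under assumptions.** The documents give no absorption or elimination rate. I assume one compartment with first-order absorption, absorption half-life 1-3 days and elimination half-life 15-25 days. Concentration, in units of FD/V, is

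C(t) = ka/(ka − ke) × (exp(−ke·t) − exp(−ka·t)), with each rate equal to ln 2 divided by its half-life.

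AUClast uses the linear rule on the rise and the log rule on the fall.

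Worked case: half-lives 1 and 15 days, samples 7, 21 and 28 days after dosing.
- ka = 0.693, ke = 0.0462, ka/(ka − ke) = 1.071.
- C(4) = 0.824, C(7) = 0.767, C(21) = 0.406, C(28) = 0.294.
- True AUC from 0 to 28 days is 15.28. True Cmax is 0.824, at 4.2 days.
- Without the early sample: 0.767 × 7/2 = 2.68 for days 0-7, then 7.94 and 2.43. The total is 13.05, a ratio of 0.854.
- With a sample at day 4: 0.824 × 4/2 = 1.65 for days 0-4 and 2.39 for days 4-7, then 7.94 and 2.43. The total is 14.41, a ratio of 0.943.
- Gap: 0.943 − 0.854 = 0.089, about 9 points.
- Cmax: 0.767/0.824 = 0.931 without the early sample and 0.999 with it, a gap of about 7 points.

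The same calculation elsewhere in the range (absorption/elimination half-life in days):

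| Half-lives | AUC ratio without / with day 4 | Gap | Cmax ratio without / with day 4 |
|---|---|---|---|
| 1 / 15 | 0.854 / 0.943 | 9 points | 0.931 / 0.999 |
| 1.5 / 20 | 0.893 / 0.957 | 6 points | 0.994 / 0.994 |
| 2 / 20 | 0.904 / 0.956 | 5 points | 0.999 / 0.999 |
| 3 / 25 | 0.920 / 0.952 | 3 points | 0.949 / 0.949 |

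**4. Uncertain later sampling days.** Column positions in the extracted schedule table are unreliable after Day 8. I repeated step 3 with later samples at 7/21, 7/14/28 and 7/28 days, each against the true AUC to the last sample. Over all four layouts the gap is 3 to 10 points; the largest is 0.932 − 0.827 under 7/21. Early-sample cohorts are themselves 3-9% low (ratios 0.913-0.971).

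**5. Wider assumptions.** With ka 0.15-1.0 per day, elimination half-life 10-21 days and the early sample at 2-5 days, the AUClast gap is about 2 to 19 points, always in the same direction.

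**The case against.** The strongest reply is that the numerical effect is small and rests on assumed rates. For absorption half-lives of 2 days or more, the true peak comes at 6.7 days or later. A sample at any of days 2-5 then changes neither observed Cmax nor observed Tmax. At 1.5 days the gain in Cmax is at most 1.5 points. Early-sample cohorts also understate AUC. Cohorts have 2-4 participants, expandable to 12, the summaries are descriptive, and nothing shows that a gap of this size would be visible against variation between participants. The SAP also lists, summarises and plots concentrations by cohort, so a difference in sampling stays traceable. Dose-escalation decisions are untouched.

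All of this stands, and it limits the size. It does not reconcile the cohort lists or justify pooling two schedules within a dose level.

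Two stronger readings are tempting. A reader might infer that Cmax and Tmax in the affected cohorts are simply biased. The documents do not support that, because it depends on an absorption rate they do not give. A 5% shortfall in Cmax, as at half-lives of 3 and 25 days, is the same with or without the early sample.

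A reader might also infer that the SAP deliberately overrides the protocol. The SAP describes the protocol of 16 March 2018, which is not available here, and the NCA text of the current protocol may have been edited since. An SAP that was not updated is equally plausible. SAP Section 2 does claim precedence and undertakes to identify substantial differences, and this one is not identified.

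**Conclusion.** The mismatch is exact and needs no model. The SAP plans first-dose NCA in three antibody-by-cohort groups that were run (tremelimumab 4A and 5A, sasanlimab 6A), which the current protocol leaves out and which have no post-dose sample before Day 8. It then pools them with early-sample cohorts at 40 mg tremelimumab and 300 mg sasanlimab.

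The consequence is modest. Under the assumed model and a day-4 early sample, AUClast is about a further 3-10 percentage points low in the affected cohorts. Cmax is lower, by up to about 7 points, and Tmax later only if the absorption half-life is near 1 day. These sizes rest on assumed rates and uncertain later sampling days. The finding concerns secondary PK summaries, and correcting the SAP is worthwhile because it is cheap.

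**What to change.** Align SAP 8.2.1.1 with protocol 9.6.1.1 and 9.6.1.2: derive first-dose NCA parameters for tremelimumab in 3A and 6A only, and for sasanlimab in 4A and 5A only. Every dose level run is kept (40 and 80 mg tremelimumab; 130 and 300 mg sasanlimab). For tremelimumab in 4A/5A and sasanlimab in 6A, report concentrations and Ctrough.

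If the sponsor prefers to keep NCA in those cohorts, present the parameters by cohort, do not pool them by dose with early-sample cohorts, flag the missing Day 3-6 sample in the tables, and record the departure from the protocol as SAP Section 2 requires.

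The restriction is a wording change. Its cost is fewer participants in the parameter summaries: 40 mg tremelimumab would rest on 3A alone and 300 mg sasanlimab on 5A alone.
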